### **Data and Safety Monitoring Plan**

The risks of this study are minimal compared to trials involving biomedical interventions or procedures. We have developed a data and safety monitoring plan in accordance with this lower level of risk. Primary responsibility for data and safety monitoring will be assumed by the principal investigator ([name]).

Data risks and monitoring: The primary data risks are inadequate quality of data collection, unacceptable intervention acceptance rates, data security, and unintended harm of health messaging. To address these risks, the principal investigator will review data quality and intervention acceptance rates on a quarterly basis. If risks are realized, investigators will consider stopping the study and/or taking appropriate steps to improve study quality and ensure adequate power. Electronic data security will be maintained with password protected computers accessible only to relevant study staff. Transcribed data will be secured in designated locked facilities at RHSP. Any data risk will be reported in a timely fashion to the appropriate IRBs. Any possible harm reported by participants will be immediately addressed by the PI and study team and reported to appropriate IRBs.

Safety risks and monitoring: The primary risks in this study are social harms related to loss of confidentiality and embarrassment and sensitivity related to discussions about sensitive topics such as health and sexual behaviors. To minimize these risks, we will perform informed consent and utilize a strong training curriculum that emphasizes strict confidentiality and protecting against inadvertent

Date: March 30, 2015

Principal Investigator: [name], MPH

Application Number: IRB00065934

disclosure. Additionally, we will ensure that training emphasizes caring, non-judgmental, and non-threatening approaches to the questioning, counseling, and teaching of participants. We will train study-related personnel to stop their tasks if the participant appears to be in distress and to contact higher-trained staff if distress is noted. Any breaches of confidentiality will be considered an adverse event and immediately reported to the principal investigator. Should any adverse event occur which may be related to study activities, an adverse event form will be completed by study staff and the event immediately reported to the principal investigator.

Adverse Events: Adverse events will be routinely monitored, collected, and reported by study staff and the principal investigator according to NIH guidelines. Staff will be trained to complete an adverse event form which will be filed and electronically sent to the principal investigator for review. The principal investigator will ensure that study staff are appropriately trained on adverse event reporting. Adverse events will be reported promptly to the appropriate IRBs.

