**Table 2: Examples of EMI responses.**

EMA Data Collected	EMI Response
Any “negative” health behavior entered.	“Today is a great day to start being healthy.” “You can make a difference in your health.” “You have people around you who care about you.”
Did you eat any vegetables? NO	“Eating a mixed diet (meats and vegetables) is a healthy way to go.”
Participant enters a geolocation previously associated with smoking.	“There are better things to spend money on than cigarettes.” “Smoking causes lung cancer.”

*Cultural Adaption, Language, and Literacy Formative Work.* Prior to beginning formal recruitment, we will test the appropriateness of our questions and messaging in terms of cultural adaptation, clarity, and meeting literacy requirements. Specifically, we will use our initial list of proposed questions and messages and then ask potential participants (~10) in the study whether the questions and messaging are clear, acceptable, and correctly understood by them. We will then refine questions and messaging as needed.

**Secondary Objective: To assess processes, facilitators, and barriers to EMAI-**These results will inform future EMAI implementation, scale-up, and sustainability questions. We will utilize a mixed methods (quantitative and qualitative) approach involving process indicator analyses, in-depth interviews (IDI), and focus group discussions (FGD).

Quantitative Methods and Analytic Plan for Process Measures. We will gather process data during EMAI implementation to include: *EMA prompt response rate, form completion rates, out-of-network time, malfunctions, down time, and device retention.* Process measures analyses will be exploratory in nature. We will use descriptive statistics, as well as explore associations with moderating/mediating

Date: March 30, 2015  
 Principal Investigator: [name], MPH  
 Application Number: IRB00065934

factors such as gender and age using Chi-square, Fisher’s exact test, and multivariate regression methods as appropriate.

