**Secondary Objective: To compare EMAI-collected with traditional questionnaire-collected data-**  
 We will describe and compare EMAI versus traditional questionnaire-collected data.

**Methods.** All study participants will be administered a traditional paper-based questionnaire at the completion of the 30 day follow-up period and a similar questionnaire after the 60 and 90 day follow-up periods. This questionnaire will assess satisfaction and acceptability of the participant’s experience using EMAI. Additionally, the questionnaire will ask the same behavioral questions as the EMAI application, but ask participants to recall these behaviors over the past 30 days, e.g. over the past 30 days, how many days did you drink alcohol?

**Analytic Plan.** Responses to traditional questionnaire data will be compared with EMAI collected data using descriptive statistics such as percent agreement, Kappa statistic, scatter plot correlation graphs, mean within-pair differences, coefficient of variation, and Bland-Altman plots. Successful completion of this aim will generate important preliminary evidence on EMAI acceptability and reliability to support future NIH studies.

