Protection of confidentiality: *Research materials:* Materials will include the interviews, consent forms, and mobile phone logs of all activity conducted through the mHealth application. In order to preserve confidentiality, informed consent documents – which by definition include the participant's name - are retained in locked filing cabinets and secure store rooms, accessible only to senior investigators or designated staff. No personal identifiers will be attached to the questionnaire or samples. Electronic data sets and clinical readouts are downloaded into password protected computers, and individual identifiers are stripped. Names linked to study IDs are stored in a separate, password protected electronic file, on a computer and server accessible only to authorized senior personnel. All RHSP research staff have received extensive human subjects/research ethics training, including the need for complete confidentiality. Participant entered EMAI data will be encrypted at all times, be it on the phone, with data transfer, or sitting on the server. The application and server access will be password protected. If a phone is lost or stolen, we will have the ability to remotely wipe the phone of all data and render it inoperable. All interviews will be conducted in private or, if appropriate, as a focus group. If a breach of confidentiality occurs, we will report to the appropriate IRBs according to NIH guidelines. The principal investigator will discuss any breaches of confidentiality and intervene as necessary to decrease the risk of future breaches.

Avoidance of social harm: We will counsel participants on the need to be discrete with their smartphones to avoid risk of being targeted for theft or exploitation. We will attempt to use locally available smartphones to minimize the novelty of participants using these devices. We will teach participants to immediately contact study staff if they have any negative experiences and they will be able to return the phones and quit the study at any time.

Date: March 30, 2015  
Principal Investigator: [name], MPH  
Application Number: IRB00065934

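### The plan describes no scheduled question about harms, so social harms may be under-recorded and not comparable between arms, although visits at Days 30, 60 and 90 are already planned

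*Combined protocol and SAP*

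**What the plan says.** All references are to the combined protocol and SAP.

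**Harms named.** Section 8 (Safety risks and monitoring) says: "The primary risks in this study are social harms related to loss of confidentiality and embarrassment and sensitivity". Section 8 (Potential risks/harms) adds theft or exploitation of people carrying a smartphone, and harm from inaccurate health advice.

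**How a harm reaches staff.** Section 8 (Avoidance of social harm): "We will teach participants to immediately contact study staff if they have any negative experiences". Section 8 also says the team can be reached by mobile phone, and that staff stop and escalate if they see distress during their tasks.

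**What is then recorded.** The Data and Safety Monitoring Plan contains four statements:
- "Should any adverse event occur which may be related to study activities, an adverse event form will be completed by study staff"
- "Any breaches of confidentiality will be considered an adverse event and immediately reported to the principal investigator"
- "Any possible harm reported by participants will be immediately addressed by the PI and study team and reported to appropriate IRBs"
- "Adverse events will be routinely monitored, collected, and reported by study staff and the principal investigator according to NIH guidelines"

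**Scheduled contacts.** Section 4 plans office visits with a questionnaire at Days 30, 60 and 90. Of its content the protocol says "This questionnaire will assess satisfaction and acceptability of the" participant's use of the application, together with recalled behaviours. The Day 60 and 90 visits are also said to cover experiences with the phone. All 120 participants have an in-depth interview after Day 90. Four focus groups of 6 to 8 people are held, two after Day 30 and two after Day 90.

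**Phone loss.** Section 4 lists, among the process measures, "malfunctions, down time, and device retention". A participant whose phone is lost or stolen forfeits incentives and gets no replacement.

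**The concern.** A harm that nobody asks about is recorded only if the participant raises it or staff notice it. The harms named here (a partner seeing answers, embarrassment, a phone being taken, trouble after following a message) are ones that people may not volunteer. For theft the plan adds a disincentive, because reporting it costs the participant the incentive.

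Two things are at stake. First, a participant harmed early may not be identified at the Day 30 or Day 60 visit, when the team could still respond. Second, a low count would be hard to interpret. The pilot is meant to inform larger randomised trials, and only the intervention arm receives messages, so message-related harm could differ by arm. Without the same question put to both arms, a difference in recorded harms cannot be separated from a difference in willingness to report. Section 9 already concludes that benefits outweigh risks, and the harm data should be able to test that.

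**Working it through.** The documents give no harm rate, harm count or safety sample size, so there is no figure of the plan's own to reproduce. The check is a comparison of the text, followed by an illustration under assumptions.

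**1. Is any scheduled contact described as asking about harm and leading to an adverse event form?**

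| Contact | Who | Described content | Linked to the form? |
|---|---|---|---|
| Day 30 questionnaire | All who continue | Satisfaction, acceptability, 30-day recall of behaviours | Not stated |
| Day 60 and 90 questionnaires | All who continue | As above, plus experience with the phone | Not stated |
| Focus groups after Day 30 | 2 × 6 = 12 to 2 × 8 = 16 of 120 | Guide topics include confidentiality and challenges | Not stated |
| Interviews after Day 90 | All 120 planned | Same guide topics | Not stated |
| Quarterly review by the principal investigator | Not applicable | Data quality and intervention acceptance rates | Harms not mentioned |

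No row both asks about harm and leads to a form. Section 7 plans no table of harms by arm.

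**2. Which events get a form?** The form rule covers events with a possible relation to the study. Confidentiality breaches are adverse events automatically. Any possible harm that a participant reports goes to the IRBs, with no relatedness condition. The general Adverse Events paragraph also has no such condition, but gives no question, schedule or method. Staff cannot tell from these four statements whether an event they think unrelated needs a form.

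**3. Theft.** It is a named risk, but it is not declared an adverse event. The only related measure is device retention.

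**4. Illustration.** Inputs from the documents: 120 participants randomised 1:1, so 60 per arm. Assumed: true harm rate r (share of participants with a harm) and capture share c (share of those harms recorded), with participants independent. Then P(no recorded event) = (1 − r·c)^n.

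| r | c | n = 120 | n = 60 |
|---|---|---|---|
| 2% | 1 | 0.98^120 = 0.089 | 0.98^60 = 0.298 |
| 2% | 0.5 | 0.99^120 = 0.299 | 0.99^60 = 0.547 |
| 2% | 0.25 | 0.995^120 = 0.548 | 0.995^60 = 0.740 |
| 5% | 1 | 0.95^120 = 0.002 | 0.95^60 = 0.046 |
| 5% | 0.5 | 0.975^120 = 0.048 | 0.975^60 = 0.219 |
| 5% | 0.25 | 0.9875^120 = 0.221 | 0.9875^60 = 0.470 |

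For the arms, r refers to Days 31 to 90, because randomisation follows the Day 30 questionnaire.

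If no event is recorded in 120 people, the exact one-sided 95% upper limit on the recorded rate is 1 − 0.05^(1/120) = 2.5%. With full capture that is also the limit on the true rate. With half captured the limit on the true rate is 0.02466 / 0.5 = 4.9%. The capture share therefore decides what a zero count means, and nothing in the plan lets a reader judge it.

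**The case against.** The other side has real force on four points.

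**Recording is wider than one sentence suggests.** A reader might infer from the form rule that harms are logged only when thought study-related. The documents do not support that. The threshold is only possible relation, confidentiality breaches count automatically, participant-reported harms go to the IRBs unfiltered, and the Adverse Events paragraph has no relatedness limit. What stands is that these statements are not reconciled.

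**Reporting is not purely spontaneous.** Staff may observe distress, the later questionnaires cover phone experience, some participants join focus groups after Day 30, and all are due an interview. A missing phone is also hard to overlook, since phones are returned at Day 90. But the Day 30 focus groups reach only 12 to 16 people in a group setting, the interviews come after follow-up ends, and neither is tied to the form. Knowing that a phone is missing does not record that its holder was robbed.

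**The instruments are not in the documents.** A harm item in the questionnaires or interview guide cannot be ruled out. The protocol's description of the questionnaires mentions none.

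**Proportionality.** The plan says monitoring was scaled to low risk, and the study has no safety objective. At a 5% rate only 60 × 0.05 = 3 events per arm are expected, so even full capture would give little information between arms. Also, at 5% and half capture at least one event is recorded overall with probability 0.95, so the plan would not be blind to harm. This limits the importance of the point. It does not argue against a few questions at visits that already take place.

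**Conclusion.** The point holds as a gap in ascertainment. The plan describes no scheduled harm question, relies mainly on participants coming forward, does not link its solicited contacts to the adverse event form, tracks theft only through device retention while penalising the victim, and leaves its recording rules unreconciled. Social harms may therefore be under-ascertained and not comparable between arms.

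A reader might go further and conclude that the pilot will undercount harms. The documents do not support that: they give no harm rate and no capture share, and the questionnaires are unseen. Nor can it be said that every participant attends the three visits. Attendance is planned, and anyone may quit.

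The size of any undercount cannot be derived. The illustrative probabilities rest wholly on assumed rates of 2% to 5% and assumed capture of 25% to 100%. No planned analysis is invalidated. The change is nevertheless worth making, because it serves participant safety and costs little.

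**What to change.** 1. Add about five fixed yes/no items to the existing Day 30, 60 and 90 questionnaires, asked privately and identically in both arms: phone taken or demanded; someone saw answers or messages; conflict with partner or family; distress from the questions; a problem after following a message. Ask the Day 30 items before randomisation.
2. Complete an adverse event form for every positive answer, every phone loss or theft, and every harm disclosed in an interview or focus group. Record relatedness afterwards, as a separate field.
3. Reconcile the form rule in Safety risks and monitoring with the Adverse Events paragraph, so that one rule says which events get a form.
4. Add to Section 7 a descriptive table of harms by arm and by source (solicited or spontaneous), with Day 30 as the pre-randomisation reference and the number of people asked at each visit as the denominator.

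The cost is a few minutes per visit and more minor events to file. No extra visits or staff are needed. People who quit or do not return will still not be asked, and the denominators will show how many.

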## 9. Benefits

**Probable benefits of the proposed research to participants and for society.** Subjects in this study may benefit from positive health messaging which may modify their health behaviors in a beneficial direction. If this intervention is demonstrated to be beneficial, there are potential benefits to the larger society and public health arena. For these reasons, the potential benefits outweigh the relatively minimal risks of this study.

**Importance of knowledge to be gained.** This is the first study to our knowledge of EMAI in sub-Saharan Africa. If this novel data collection and intervention method is proven to be feasible and acceptable, it could serve as an innovative platform for the future delivery of real-time, tailored, geolocated mHealth interventions for any disease at any stage in the continuum of health care and prevention, a potentially profound method for improving health.

## 10. Payment and Remuneration

We will provide incentives, given after completing each questionnaire, to optimize response rates. Overall, compensation will be approximately \$30 over 90 days, given in three separate increments after Days 30, 60, and 90. If a participant fails to complete at least 80% of the prompts, they will forfeit their compensation.

Participants are also provided compensation for their participation in RHSP/RCCS activities and will receive this compensation per current RHSP/RCCS guidelines (currently a lump sum of about \$4 for completing one survey round).

## 11. Costs-Not applicable.

Date: March 30, 2015

Principal Investigator: [name], MPH

Application Number: IRB00065934

